**Title: PREVENTING METABOLIC SYNDROME IN MORBID
OBESITY WITH RESISTANCE TRAINING: REPORTING NON-RESPONDER
PREVALENCE**

ID: RP08042019

DATE: April 11, 2019

Study Documents

Scientific background: The prevalence of metabolic syndrome (MetS) and cardiovascular disease is expected to rise along with the global obesity epidemic [1]. MetS is a cluster of clinical risk factors, including abdominal (visceral) obesity, hypertension, elevated serum triglycerides, low serum high-density lipoprotein (HDL) and hyperglycaemia [2]. Additionally, MetS is also associated with a pro-inflammatory state that leads to an altered physiological balance of adipokines, insulin resistance, endothelial dysfunction and a pro-atherogenic state [3], that increase the cardiovascular risk when population have more fat as the obesity state [4]. The morbid obesity is considered as a chronic disease highly-related with MetS development [5]. The MetS for example, significantly decreases the life expectancy of individuals with morbid obesity [4] and increases the disease burden and economic costs associated with healthcare [6]. In this sense, more recently, there was reported that body mass index (BMI) and fat distribution showed higher associations with inflammation, fat indices, and more prevalence of MetS in morbidly obese subjects [7], claiming for an early prevention of the MetS in the morbid obese state. Exercise training has proven to be effective in inducing a clinically significant weight loss and reducing cardiovascular risk [8]. Exercise have reported to be associated with increased muscle mass, decreased body fat, and improved metabolic profile (i.e., improved glucose control and lipid levels) [9].

Additionally, exercise training in MetS patients was also associated with a significant reduction in high-sensitivity C reactive protein, and insulin resistance, but independent of weight loss [10], being this last effect (i.e., weight loss) a non-necessary aim into morbid obese patients. However, considering that the cardiorespiratory fitness (CRF) have been reported to be a strong predictor of overall health, exercise training may improve CRF in patients with MetS [11, 12], and thus we speculate that the CRF related outcomes such as the walking perform can be relevant for the health in obese patients at risk of MetS. Additionally, the resistance exercise training (RT, i.e., a particular exercise training modality consisting in stimulating muscles using external weights), may help to reduce health markers as systolic blood pressure (SBP) in obese patients with MetS risk factors [13]. In addition, supervised RT improved muscle strength and functional capacity in patients with obesity undergoing bariatric surgery [14]. However, although RT has been widely studied in obesity [15], there is little information in the morbid obesity. On the other hand, there is poor knowledge similarly, about the interindividual variability to exercise training in terms of responders and non-responders (NR). For example, as in reducing fat markers, we have shown that more baseline fat (overweight, obesity) have showed higher fat decreases and thus less NR, we speculate that morbid obese patients could decrease more both fat and MetS markers than other peers with less fat as those with obesity. Objectives: to determine the effects of a resistance training programme (RT) in preventing or attenuating metabolic syndrome (MetS) in patients with morbid obesity. A second aim was to report the prevalence of NR in terms of improvements in MetS markers and other co-variables considered. Design: An experimental, and non-randomized control clinical study. Methods: In an experimental clinical trial, obese and morbid obese patients will be invited for participating in a lifestyle study including resistant training during 20 weeks for preventing MetS in this cohort. Participants will be

recruited from the morbid obesity (Temuco, Chile), during two months by phone invitation. The sample size will be determined in accordance with the study's feasibility recruitment, and a previous pilot study where it was determined the effects of a RT programme on anthropometric parameters, muscle function and metabolic profile and nutritional in the potential morbid obese patients [8]. The study will be completed in accordance with the Declaration of Helsinki and was approved by the Ethical Committee of the Universidad de La Frontera, Temuco, Chile. Patients and Recruitment: The inclusion criteria will be as follows: i) older than 18 and younger and =65 years of age (i.e., 65 y is the retirement age in women in Chile), ii) daily activities including walking, physical autonomy, iii) medical authorization by a physician, and iv) body mass index (BMI) =35 kg/m², according to BMI, general population is classified: class II obesity (BMI =35.0-39.9 kg/m²), class III - extreme obesity or morbid obesity (BMI =40 kg/m²) [16, 17]. Exclusion criteria will be: i) physical limitations (e.g., restricting injuries of the musculoskeletal system, or dependent of a third person), ii) exercise-related dyspnoea or respiratory alterations, iii) chronic heart disease with any worsening in the last month, and iv) an adherence rate of less than 80% of the total interventions (excluded from the statistical analyses).

REFERENCES

- [2] Alberti KG, Eckel RH, Grundy SM, Zimmet PZ, Cleeman JI, Donato KA, et al. Harmonizing the metabolic syndrome: a joint interim statement of the International Diabetes Federation Task Force on Epidemiology and Prevention; National Heart, Lung,

and Blood Institute; American Heart Association; World Heart Federation; International Atherosclerosis Society; and International Association for the Study of Obesity. *Circulation*. 2009;120:1640-5.

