

Statistical Analysis Plan (SAP): We will apply 2 main forms of statistical analyses a) to report the pre-post changes in mean terms, and b) to report the results according with the inter-individual responses based on the technical error criteria, where according with the error calculated in the three previous measurements registered by the sample that was voluntary. Thus, for example, we will classify the subjects in responders and non-responders by the technical error of measurement, and additionally, we will classify the subjects according with a responder and non-responder clinical criteria, where we will classify as responders to all subjects who can be able of changing an initial adverse clinical altered profile for a healthy new classification. Thus, the specific statistical methods that we hope to apply for each analysis are; test of normality and homoscedasticity assumptions using Shapiro-Wilk and Levene's tests, the Student's t test for the identification of differences at baseline. An ANCOVA will be conducted (for potential confounders outcomes) in those altered baseline differences outcomes. We also hope to apply the repeated measures of two-way (group, time) to assess occurrence of an actual training effect [i.e., $p < 0.05$ for the interaction (group \times time) for the different study outcomes]. Among the specific statistical methods we hope to apply the Bonferroni post hoc test we hope to apply when we can be seen test differences among groups. Similarly, we hope to apply the Cohen's d test in order to detect effect size, using the threshold values of 0.20, 0.60, 1.2, and 2.0 for small, moderate, large, and very large effects, respectively [18], with 95% confidence intervals (CI). The alpha level was fixed at $P < 0.05$ for statistical significance.

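### Group × time significance is taken to show a training effect in a non-randomised study that does not define its groups, control condition or allocation rule

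*Combined protocol and SAP*

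**What the plan says.** The Design statement in the protocol reads "An experimental, and non-randomized control clinical study". Under Methods, "obese and morbid obese patients will be invited for participating in a lifestyle study including resistant training during 20 weeks"; recruitment is from one source, "during two months by phone invitation". One set of eligibility criteria applies to everyone. Nowhere do the documents define the groups, describe the control condition, or say who or what decides group membership. No sample size is given: "The sample size will be determined in accordance with the study's feasibility recruitment, and a previous pilot study".

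In the Statistical Analysis Plan, a two-way repeated-measures analysis (group, time) is to be used "to assess occurrence of an actual training effect", judged by p<0.05 for the interaction on the various outcomes. The protection against non-comparable groups has two steps. The first is "the Student's t test for the identification of differences at baseline". The second is conditional on it: "An ANCOVA will be conducted (for potential confounders outcomes) in those altered baseline differences outcomes". No covariates are named. On the error level: "The alpha level was fixed at $P < 0.05$ for statistical significance".

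**The concern.** A group × time interaction shows that mean change differed between the groups. It shows that training caused the difference only if the groups would otherwise have changed alike. Randomisation would give that on average. Here it is left to an allocation process that the plan does not describe.

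The planned safeguard has two gaps. First, the baseline t test examines outcomes, so it cannot see motivation, diet change or ability to attend, any of which could move metabolic markers over 20 weeks. Second, a significance test is a weak screen for imbalance in small groups, and adjusting only when it fires gives up precision in the outcomes where it does not.

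At stake is the primary objective, which is worded as determining the effects of the programme. A positive interaction could be reported as such an effect when the design cannot separate it from who was in each group.

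**Working it through.** **Inputs.** From the documents: alpha 0.05 (two-sided assumed, since sidedness is not stated), a pre-post comparison between groups, and ANCOVA only after a significant baseline t test. Assumed, because the documents give no figure: n per group, equal groups, the size of any bias, and the pre-post correlation ρ. The plan has no figure of its own to reproduce beyond alpha.

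**1. Interaction test under bias and no training effect.** With two time points, the group × time test is the two-sample t test on change scores. If the groups' mean changes differ by b SD of change for reasons other than training, the statistic is non-central t with df = 2n − 2 and δ = b√(n/2). The rejection rate is P(|T| > t₀.₉₇₅). Take b = 0.25, for example a factor that differs by 0.5 SD between groups and correlates 0.5 with change (0.5 × 0.5).

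| n per group | δ | df | critical t | rejection rate |
|---|---|---|---|---|
| 20 | 0.25 × √10 = 0.791 | 38 | 2.024 | 12.0% |
| 30 | 0.25 × √15 = 0.968 | 58 | 2.002 | 15.9% |
| 50 | 0.25 × √25 = 1.250 | 98 | 1.984 | 23.6% |

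Range over b, by normal approximation, at 20, 30 and 50 per group:
- b = 0.2: 9.7%, 12.1%, 17.0%
- b = 0.3: 15.8%, 21.3%, 32.3%
- b = 0.5: 35.3%, 49.1%, 70.5%

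With b = 0 the rate is 5%. The error rises with n, so recruiting more people does not help.

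**2. Baseline t test as a screen.** The same formula applies, with a true baseline imbalance of 0.5 SD. At n = 20, δ = 0.5 × √10 = 1.581 and the test is significant 33.8% of the time. At n = 30, δ = 0.5 × √15 = 1.936 and the figure is 47.8%.

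**3. Unmeasured driver, balanced baselines.** Simulation with 20,000 runs, ρ = 0.7, n = 20, and a shift of 0.3 baseline SD. SD of change = √(2 × (1 − 0.7)) = 0.775, so the shift is 0.3/0.775 = 0.39 SD of change. Rejection rates with no training effect:
- interaction test: 21.4%
- planned conditional rule: 21.0%
- ANCOVA always: 24.1%

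The baseline t test is significant in 5.1% of runs, its chance rate. ANCOVA is slightly worse because it leaves the bias in place and shrinks the residual variance around it.

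**4. Measured imbalance only.** Same simulation, 0.5 SD baseline imbalance and no other driver. Rejection rates for the interaction test, the planned rule and ANCOVA always:
- n = 20: 9.4%, 5.7%, 5.1%
- n = 30: 11.1%, 5.7%, 5.0%

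**5. Precision given up.** In baseline-SD units, the variance of a change score is 2(1 − ρ) and the ANCOVA residual variance is 1 − ρ². At ρ = 0.7 these are 0.60 and 0.51; at ρ = 0.5 they are 1.00 and 0.75. Simulated power for a true effect of 0.5 baseline SD, no bias:

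| ρ | n per group | planned rule | ANCOVA always | gain (points) |
|---|---|---|---|---|
| 0.7 | 20 | 51.0% | 56.4% | 5.4 |
| 0.7 | 30 | 69.2% | 75.2% | 6.0 |
| 0.5 | 20 | 34.0% | 42.1% | 8.1 |
| 0.5 | 30 | 48.1% | 58.9% | 10.8 |

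**The case against.** The plan openly calls itself non-randomised, and a quasi-experiment is a legitimate choice. Its wording is that the interaction serves to assess a training effect, not that significance proves one. The ANCOVA sentence mentions potential confounders and, though unclear, may be meant to reach beyond each outcome's own baseline. For a measured imbalance the planned rule nearly holds its level (step 4). Always adjusting does not cure the unmeasured problem (step 3). All of this stands, and it limits the point to the causal reading, the missing definitions and the lost precision.

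Three stronger readings are tempting, and the documents support none of them.
- A reader might infer that motivated patients choose training. The documents do not say who decides, so self-selection is plausible but not documented. Blinding is not mentioned either way.
- A reader might infer that every participant could have entered either group and should simply have been randomised. With the groups undefined, that is not established. The protocol speculates that morbidly obese patients will improve more than less obese peers, and it sets out both BMI classes, so group could mean BMI class. On that reading nobody can be randomised to a group, and the interaction would not measure a training effect at all.
- A reader might say that a 0.25 SD bias exceeds the plan's own 0.20 threshold for a small effect. The SAP does not state the standardiser for Cohen's d. In baseline-SD units the bias is 0.25 × 0.775 = 0.19 at ρ = 0.7, below 0.20.

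**Conclusion.** The point holds in this form: the plan attaches a causal reading to a test whose validity depends on an allocation process it does not describe, and its safeguard cannot reach unmeasured causes of change. Under an assumed bias of 0.25 SD of change, the nominal 5% test is significant 12%, 16% and 24% of the time at an assumed 20, 30 and 50 per group with no training effect. These are illustrations. The documents give neither a sample size nor any evidence on the size or direction of bias.

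The test-then-adjust rule is a smaller fault. It costs under one percentage point of error rate for a measured 0.5 SD imbalance, and about 5 to 11 points of power for a 0.5 baseline-SD effect at 20 to 30 per group with ρ of 0.7 or 0.5. The error-rate comparison assumes that follow-up depends on baseline in the same way in both groups. If the groups regress towards different means, ANCOVA can itself be biased, which is a further reason for the softer wording.

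**What to change.** **SAP, analysis.** Replace the conditional ANCOVA and the unadjusted interaction test with one ANCOVA per outcome: follow-up value on group, that outcome's baseline value, BMI, age and sex, fitted whatever the baseline t test shows.

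**SAP, wording.** Replace the training-effect phrase with *adjusted between-group difference in a non-randomised comparison*, and state that residual confounding cannot be excluded.

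**Protocol.** Define group, the control condition, and how participants enter each group. The model above takes group to mean training against control. If it means BMI class, BMI cannot serve as a covariate in this way and the comparison should not be described as a training effect.

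**Cost.** A few degrees of freedom: residual df fall from 2n − 2 to 2n − 6, for example from 38 to 34 at 20 per group. The conclusion is also less strong. Age and BMI are already needed for eligibility. Sex is not an eligibility criterion but is trivial to record.

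Allocation from a computer-generated random list would be the stronger design if the sponsor is still free to choose it. It is a redesign that needs an ethics amendment and, if controls are offered the programme afterwards, a second 20-week delivery. It is therefore not part of this low-cost fix.

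### Removing participants with under 80% adherence from every analysis confines both aims to adherers and may understate non-responder prevalence among those who start training

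*Combined protocol and SAP*

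**What the plan says.** The last exclusion criterion under Patients and Recruitment is "iv) an adherence rate of less than 80% of the total interventions (excluded from the statistical analyses". No analysis is exempted from it.

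The Objectives set two aims: "to determine the effects of a resistance training programme (RT) in preventing or attenuating metabolic syndrome (MetS) in patients with morbid obesity", and then "A second aim was to report the prevalence of NR in terms of improvements in MetS markers" together with other variables. Neither is restricted to people who completed a given share of the programme. NR prevalence is also in the study title.

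The SAP describes two main forms of analysis. One is "to report the pre-post changes in mean terms". The other is individual response, where "we will classify the subjects in responders and non-responders by the technical error of measurement" and also by a clinical criterion (moving from an adverse to a healthy classification). The group comparison is the group-by-time interaction in a two-way repeated-measures analysis. The SAP defines no analysis population and gives no all-enrolled analysis, sensitivity analysis or missing-data method. It does not ask for the number excluded to be reported.

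The comparison group is not clearly described. Design says "An experimental, and non-randomized control clinical study". Methods says "obese and morbid obese patients will be invited for participating in a lifestyle study including resistant training during 20 weeks", and the Scientific background speculates that "morbid obese patients could decrease more both fat and MetS markers than other peers with less fat". On that wording both groups might be trained. The documents do not say how the adherence rule applies to the comparison group.

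**The concern.** A prevalence depends on its denominator, and here the denominator is filtered by something that happens during the intervention. People who attend less are plausibly those who improve less, through lower exposure or because of illness or motivation. If so, removing them lowers the reported NR figure for patients who start RT. This needs no assumption about the comparison group.

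The group-by-time comparison is exposed under narrower conditions. If the rule removes people mainly from a trained group set against an untrained one, the result overstates the effect of starting RT. If adherence is also prognostic, so that adherers would improve more even without a training effect, a benefit can appear where there is none. These are separate scenarios and are kept apart in the calculation.

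**Working it through.** **Inputs.** From the documents: the 80% threshold, the 20-week programme, the two aims, the group-by-time test and alpha of 0.05. The documents state no sample size, dropout rate, adherence rate, NR rate or effect size, so there is no figure of the plan's to reproduce. Everything below the threshold rule is assumed: share of starters excluded p = 20% or 30%; correlation r between adherence and improvement = 0, 0.3 or 0.5 (bivariate normal, lowest p on adherence dropped); reported NR among adherers = 30%; 30 or 50 per group for the simulations.

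**1. NR prevalence, independent of the comparison group.** The identity is

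NR(all starters) = (1 − p) × NR(adherers) + p × NR(excluded),

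so the understatement is p × [NR(excluded) − NR(adherers)]. The response threshold is set so that 30% of those retained are NR, and the model then gives NR among those excluded:

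| p | r | NR excluded | NR all starters |
|---|---|---|---|
| 20% | 0.3 | 50.4% | 0.8 × 30 + 0.2 × 50.4 = 34.1% |
| 20% | 0.5 | 66.0% | 0.8 × 30 + 0.2 × 66.0 = 37.2% |
| 30% | 0.3 | 49.3% | 0.7 × 30 + 0.3 × 49.3 = 35.8% |
| 30% | 0.5 | 64.3% | 0.7 × 30 + 0.3 × 64.3 = 40.3% |
| either | 0 | 30% | 30% |

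**2. Group effect, exposure only.** Assume an untrained comparison group, exclusion in the RT group only, and adherence unrelated to prognosis. If low adherers obtain a fraction f of the adherers' effect d, the effect of starting RT is d × (1 − p + p × f). With d = 0.50 SD:

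- f = 0.5: 0.50 × 0.90 = 0.45 (p = 20%) and 0.50 × 0.85 = 0.425 (p = 30%).
- f = 0: 0.50 × 0.80 = 0.40 and 0.50 × 0.70 = 0.35.

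With no training effect, simulated rejection in this scenario stays at 4.9–5.0%.

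**3. Group effect, prognostic selection with no training effect.** With exclusion in the RT group only, the spurious benefit in SD units is r × φ(z_p)/(1 − p), where z_p is the normal quantile at p and φ the normal density. The rejection rates come from a two-group t test on change, 100,000 simulated trials per setting:

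| p | r | Spurious benefit (SD) | Rejection, 30 per group | Rejection, 50 per group |
|---|---|---|---|---|
| 20% | 0.3 | 0.105 | 6.6% | 7.9% |
| 20% | 0.5 | 0.175 | 9.8% | 13.3% |
| 30% | 0.3 | 0.149 | 8.0% | 10.5% |
| 30% | 0.5 | 0.248 | 13.9% | 20.4% |

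With equal exclusion in both groups the mean difference is 0 and rejection is 5.3–6.0%.

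**4. Bounds when the excluded are not all measured.** Count unmeasured people first as all responders, then as all NR.

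- None measured: 0.8 × 30 = 24% to 24 + 20 = 44% (p = 20%); 0.7 × 30 = 21% to 21 + 30 = 51% (p = 30%).
- Half measured, with NR in those measured as in step 1: 29.0–39.0% (r = 0.3) or 30.6–40.6% (r = 0.5) for p = 20%; 28.4–43.4% or 30.6–45.6% for p = 30%. The width falls to 10 or 15 points.

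**The case against.** The best defence is that the adherers' question is the intended one. The background motivates NR as individual variability in response to exercise training, and the SAP presents the interaction test as showing whether training truly had an effect. Someone who hardly trained is arguably unexposed, not a non-responder. The restriction is also declared in advance, and putting all starters first prefers one legitimate target over another.

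Part of this stands. Response given adequate training is a legitimate question and should stay in the report. But the Objectives do not limit themselves to it, it is the only question analysed, and a reader would take the NR figure as applying to patients who begin the programme.

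It is also fair that every size rests on assumptions. The false-positive scenario in particular needs prognostic adherence, RT-only exclusion and an untrained comparison group together, so it deserves little weight. The rule refers to the interventions in total and may not be RT-only. Finally, measuring people who have stopped attending is not trivial, and where few are measured the bounds are wide and a mixed model gives limited protection. These points limit the claimed size and the benefit of the remedy. They do not supply the missing analysis.

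**Conclusion.** The concern holds. As written, the plan filters both aims on a post-baseline event and offers no analysis that would reveal the consequence. That omission is certain from the text; the direction and size of any bias are conditional.

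- NR is understated for RT starters if low adherers respond less: 4 to 10 percentage points on a reported 30% under the assumptions used, and none if they respond like the rest.
- The group effect is overstated as an effect of starting RT only if the exclusion also falls mainly on the trained group. If both groups train and lose similar people, this need not arise.
- A raised false-positive rate needs the stronger prognostic scenario.

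This is an inexpensive improvement to make, not a fatal flaw.

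**What to change.** Delete the adherence criterion as an exclusion from analysis and write the following into the protocol and SAP:

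1. Analyse all enrolled participants with a baseline value, in their group, whatever their adherence.
2. Seek the 20-week measurement regardless of adherence.
3. Use a mixed model for group-by-time and state its missing-at-random assumption, which is doubtful if non-adherers withdraw.
4. Report technical-error NR over everyone who started RT. Report clinical-criterion NR over RT starters with an adverse profile at baseline: someone healthy at baseline can never meet that criterion and would otherwise count as NR by default.
5. Give each NR figure the lower and upper bounds described above.
6. Describe the comparison group, define adherence and its application in each group, and report the number below 80% by group.
7. Keep the set with at least 80% adherence as a labelled secondary analysis.

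The cost is wording plus 20-week measurements in people who attended less. The estimated effect may be smaller, and the NR bounds will be wide if few of them are measured. The change removes the added selection; it does not remove the baseline confounding of a non-randomized design.
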